### **Vital signs:**

Vital signs will be done daily and include temperature, systolic blood pressure, heart rate, respiratory rate, and O2 saturation.

### **Radiographic or other imaging assessments:**

Chest x-ray will be done on enrollment.

### **Assessment of adverse events:**

Assessment of adverse events will be performed daily by the study team and as clinically indicated. Adverse events that have not resolved after completion of study drug administration will be followed until day 60.

Subjects with LFTs above 3x the ULN at enrollment will have LFTs checked daily during the hospitalization phase of the study.

Subjects who are discharged on study drug will receive a daily phone call until day 15 to assess for adverse events and will have safety labs drawn as per the schedule safety labs schedule on days 3, 5, 8, 11, and 15 as applicable.

#### **8.4 ADVERSE EVENTS AND SERIOUS ADVERSE EVENTS.**

##### **8.4.1 Definition of Adverse Event**

An adverse event (AE) is any untoward medical occurrence in a human subject, including any abnormal sign (for example, abnormal physical exam or laboratory finding), symptom, or disease, temporally associated with the subject's participation in research, whether or not considered related to the subject's participation in the research. In the context of FDA-required reporting, an AE means any untoward medical occurrence associated with the use of a drug in humans, whether or not considered drug related

(21 CFR 312.32 (a)).

##### **8.4.2 Definition of Serious Adverse Events (SAE)**

An adverse event (AE) or suspected adverse reaction is considered "serious" if, in the view of either the investigator or sponsor, it results in any of the following outcomes: death, a life-threatening adverse event, inpatient hospitalization or prolongation of existing hospitalization, a persistent or significant incapacity or substantial disruption of the ability to conduct normal life functions, or a congenital anomaly/birth defect. Important medical events that may not result in death, be life-threatening, or require hospitalization may be considered serious when, based upon appropriate medical judgment, they may jeopardize the participant and may require medical or surgical intervention to prevent one of the outcomes listed in this definition. Examples of such medical events include allergic bronchospasm requiring intensive treatment in an emergency room or at home, blood dyscrasias or convulsions that do not result in inpatient hospitalization, or the development of drug dependency or drug abuse.

##### **8.4.3 Classification of an Adverse Event**

###### **8.4.3.1 Severity of Event**

This study will utilize the Common Terminology Criteria for Adverse Events version 5.0 (CTCAE v5.0) for toxicity and adverse event reporting. A copy of the CTCAE v5.0 can be downloaded from the [https://ctep.cancer.gov/protocolDevelopment/electronic\\_applications/ctc.htm](https://ctep.cancer.gov/protocolDevelopment/electronic_applications/ctc.htm).

AEs will be recorded, verified, and followed until satisfactory resolution (return to baseline or, if event was not present prior to study drug initiation, grade 1 or lower).

Severity definitions found in the CTCAE v5.0 will be used for grading the severity (intensity) of AEs:

- 1) **Mild (Grade 1):** Asymptomatic or mild symptoms; clinical or diagnostic observations only; intervention not indicated.
- 2) **Moderate (Grade 2):** Minimal, local or noninvasive intervention indicated; limiting age-appropriate instrumental ADL\*

- 3) **Severe (Grade 3):** Severe or medically significant but not immediately life-threatening; hospitalization or prolongation of hospitalization indicated; disabling; limiting self-care ADL\*\*.
- 4) **Life-threatening (Grade 4):** Life-threatening consequences; urgent intervention indicated.
- 5) **Death (Grade 5):** Death related to AE.

\*Instrumental ADL refer to preparing meals, shopping for groceries or clothes, using the telephone, managing money, etc.

\*\*Self-care ADL refer to bathing, dressing and undressing, feeding self, using the toilet, taking medications, and not bedridden.

#### 8.4.3.2 Relationship to Study Intervention

All adverse events (AEs) must have their relationship to study intervention assessed by the investigator or designee who examines and evaluates the participant based on temporal relationship and his/her clinical judgment. The degree of certainty about causality will be graded using the categories below. In a clinical trial, the study product must always be suspect.

- **Definitely Related** – There is clear evidence to suggest a causal relationship, and other possible contributing factors can be ruled out. The clinical event, including an abnormal laboratory test result, occurs in a plausible time relationship to study intervention administration and cannot be explained by concurrent disease or other drugs or chemicals. The response to withdrawal of the study intervention (dechallenge) should be clinically plausible. The event must be pharmacologically or phenomenologically definitive, with use of a satisfactory rechallenge procedure if necessary.
- **Probably Related** – There is evidence to suggest a causal relationship, and the influence of other factors is unlikely. The clinical event, including an abnormal laboratory test result, occurs within a reasonable time after administration of the study intervention, is unlikely to be attributed to concurrent disease or other drugs or chemicals, and follows a clinically reasonable response on withdrawal (dechallenge). Rechallenge information is not required to fulfill this definition.
- **Possibly Related** – There is some evidence to suggest a causal relationship (e.g., the event occurred within a reasonable time after administration of the trial medication). However, other factors may have contributed to the event (e.g., the participant's clinical condition, other concomitant events). Although an AE may rate only as “possibly related” soon after discovery, it can be flagged as requiring more information and later be upgraded to “probably related” or “definitely related”, as appropriate.
- **Unlikely to be related** – A clinical event, including an abnormal laboratory test result, whose temporal relationship to study intervention administration makes a causal relationship improbable (e.g., the event did not occur within a reasonable time after administration of the study intervention) and in which other drugs or chemicals or

underlying disease provides plausible explanations (e.g., the participant's clinical condition, other concomitant treatments).

- **Not Related** – The AE is completely independent of study intervention administration, and/or evidence exists that the event is definitely related to another etiology. There must be an alternative, definitive etiology documented by the clinician.]

#### 8.4.3.3 Expectedness

The site principal investigator will be responsible for determining whether an adverse event (AE) is expected or unexpected. An AE will be considered unexpected if the nature, severity, or frequency of the event is not consistent with the risk information previously described for the study intervention in the package insert or investigator's brochure.

#### **8.4.4 Time Period and Frequency for Event Assessment and Follow-Up**

For this study, all grade 3 and 4 AE, clinically significant laboratory abnormalities, and all SAEs occurring from the time the informed consent is signed through the Day 60 visit will be documented, recorded, and reported in an NHLBI-approved research database. All other AEs will be collected in the subject's medical records.

The occurrence of an AE or SAE may come to the attention of study personnel during study visits and interviews of a study participant presenting for medical care, or upon review by a study monitor.

All reportable AEs including local and systemic reactions not meeting the criteria for SAEs will be captured on the appropriate CRF. Information to be collected includes event description, time of onset, clinician's assessment of severity, relationship to study product (assessed only by those with the training and authority to make a diagnosis), and time of resolution/stabilization of the event. All AEs occurring while on study must be documented appropriately regardless of relationship. All AEs will be followed to adequate resolution.

Any medical condition that is present at the time that the participant is screened and until participant receives the first dose of study drug will be considered as baseline and not reported as an AE. AE occurrence will be assessed as any change from baseline in any medical condition that results in worsening in severity and/or frequency of the medical condition, whether or not considered related to study medication.

Changes in the severity of an AE will be documented to allow an assessment of the duration of the event at each level of severity to be performed. AEs characterized as intermittent require documentation of onset and duration of each episode.

#### **8.4.5 Adverse Event Reporting**

Information on AEs will be recorded on the appropriate CRF. All clearly related signs, symptoms, and results of diagnostic procedures performed because of an AE should be grouped together and recorded as a single diagnosis. If the AE is a laboratory abnormality that is part of a

*Abbreviated Title: Fostamatinib for COVID*

*Version Date: 09/17/2020*

clinical condition or syndrome, it should be recorded as the syndrome or diagnosis rather than the individual laboratory abnormality. Each AE will also be described in terms of duration (start and stop date), severity, association with the study product, action(s) taken, and outcome.

Disease related events are still being determined as COVID-19 is a new disease however we know that COVID-19 can lead to: (Berlin, Gulick & Martinez, 2020)

- Thromboembolism (Deep venous thrombosis, pulmonary emboli)
- Cardiac (myocarditis, cardiogenic shock, takotsubo cardiomyopathy)
- Renal (acute kidney injury, proteinuria)
- Neurological (ageusia, myalgia, anosmia, stroke, headache)
- Gastrointestinal (diarrhea, weight loss, anorexia)

Due to the overlap of expected GI symptoms in subjects receiving fostamatinib, GI symptoms are highly likely to have at least a possible attribution to the study drug.

#### **8.4.6 Serious Adverse Event Reporting**

The study investigator will report any SAE to the Data Coordinating Center (DCC)/study sponsor (NHLBI) no later than 72 hrs after the investigator becomes aware of the SAE, whether or not considered study-intervention related, including those listed in the protocol or package insert and must include an assessment of whether there is a reasonable possibility that the study intervention caused the event.

All SAEs will be followed until satisfactory resolution or until the site investigator deems the event to be chronic or the participant is stable. Other supporting documentation of the event may be requested by the Data Coordinating Center (DCC)/study sponsor and should be provided as soon as possible.

SAEs from all sites will be reported to the IRB of record (NIH intramural IRB) in accordance with the Policy 801. The sites should report SAE locally in accordance with institutional requirements.

IND safety reports will be submitted to FDA by the IND sponsor in accordance with 21 CFR 312.

Data Coordinating Center (DCC)/study sponsor (NHLBI) will provide Rigel with copies of all IND Safety Reports concurrently with their submission to the FDA. The IND Safety Reports should be sent to the following email or fax:

**Email:** [[contact]](mailto:[contact])

**[contact]

The site may contact Rigel Drug Safety at the above fax/e-mail with questions regarding reporting of SAEs.

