**Study Duration:**

[figure not shown]
This study will enroll over 2-3 months and it will take another 1 month for data analysis.

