### **5.6 STRATEGIES FOR RECRUITMENT**

This is a multi-site study and subjects will be enrolled at the NIH Clinical Center, Inova Fairfax and Alexandria hospitals. Hospitalized participants will be recruited from within NIH and from the Inova hospitals.

A written strategic recruitment plan will be authored by the NHLBI Patient Recruitment Office (PRO) and ongoing regular recruitment-focused meetings will be held with the PRO and study staff and partners to ensure the study is meeting enrollment projections. If enrollment projections

*Abbreviated Title: Fostamatinib for COVID*

*Version Date: 09/17/2020*

are not being met, a strategy to boost enrollment will be implemented, and may include local news media coverage and live social media events.

Source of participants include inpatient hospital setting, outpatient clinics, and general public. The participants may also be recruited via self-referral, from in-patient services of regional hospitals and from outpatient settings.

Participants may be recruited through the use of:

- Flyers, documents/info cards, etc. for in-hospital use with patients and family;
- Recruitment advertisements and writeups placed in the NIH Record, NIH websites, the Clinical Center News;
- ResearchMatch.org;
- Newspaper writeups (print and digital) in local newspapers or outlets;
- NIH email listservs;
- Media interviews with investigators;
- NIH social media on Facebook and/or Twitter;
- ClinicalTrials.gov, Clinical Center “Search the Studies” website, NHLBI website, and NIH CC study recruitment page facilitated by CC communications office;
- Paid, targeted advertising, including digital social media ads, to local public population may be done led by the NHLBI digital communications specialist.
- A letter to physicians about the study may be provided to area ICUs and hospitalist groups.
- Hospital partners will be provided with written study materials, and in-service sessions by the study PI to educate and inform about the study.

There are no restrictions based on gender, race or ethnicity, or non-English speaking subjects.

All advertising/recruitment language will be IRB reviewed/approved prior to posting/using. Recruitment materials may be translated from English into other languages, including Spanish. Anticipated accrual rate is approximately 25 patients per month.

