## **Reports to the DSMB**

The NHLBI Lung DSMB as the independent data safety monitoring committee will review and approve the protocol before the enrollment. SAEs that meet the definition of an Unanticipated Problem will be submitted to the DSMB within 7 days of the investigator being notified of the event. DSMB will have access to safety data upon request any time. The monitoring plan will be developed and approved by the DSMB before enrollment. Additionally, the DSMB will be available for ad hoc reviews for AE/SAE, or safety concerns. The study will not stop enrollment awaiting these DSMB reviews, though the DSMB may recommend temporary or permanent stopping of enrollment based on their safety reviews.

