### **9.3.6 Planned Interim Analyses**

Interim safety analysis will be performed as requested by the by the NHLBI appointed, independent DSMB. Stopping guidelines will be evaluated if excess deaths or SAEs occur in the fostamatinib arm compared to the placebo arm. The number of interim monitoring looks and the stopping boundary based on the differences in the mortality rate and SAE between the two study arms will be developed and approved by the DSMB before the study enrollment. DCC will monitor the stopping boundary to alert DSMB if the stopping boundary is reached and have DSMB make further evaluation and recommendation about stopping the study due to safety reasons.

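### Section 8.4.6 gives sites the same 72 hours to report deaths and life-threatening SAEs as any other SAE, although the DCC must watch a mortality and SAE boundary; a 24-hour first notice would be a cheap improvement

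*Combined protocol and SAP*

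**What the plan says.** - **Reporting limit.** Section 8.4.6 has the investigator report any SAE to the DCC/sponsor "no later than 72 hrs after the investigator becomes aware of the SAE, whether or not considered study-intervention related". The report must include a causality assessment.
- **What counts as an SAE.** Under Section 8.4.2 an event is serious if "it results in any of the following outcomes: death, a life-threatening adverse event, inpatient hospitalization", among other outcomes. Deaths and life-threatening events therefore fall under the 72-hour limit, and no other section gives them a shorter one.
- **The boundary.** Section 9.3.6 leaves the number of looks and "the stopping boundary based on the differences in the mortality rate and SAE between the two study arms" to be settled with the DSMB before enrolment starts. It then states: "DCC will monitor the stopping boundary to alert DSMB if the stopping boundary is reached". The DSMB evaluates further and makes a recommendation.
- **The other numeric deadline.** Under Reports to the DSMB (within Section 8.4.6), SAEs that are Unanticipated Problems "will be submitted to the DSMB within 7 days of the investigator being notified". The same text makes the DSMB available for ad hoc reviews and says that enrolment carries on during them.
- **Pace.** Section 5.6 states: "Anticipated accrual rate is approximately 25 patients per month". The synopsis, under Study Duration, states: "This study will enroll over 2-3 months". Section 9.1 plans about 60 patients, randomised 1:1.

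**The concern.** The DCC both receives the 72-hour reports and watches the boundary. As far as the boundary depends on those reports, it is only as current as they are. Safety is the primary objective, Section 2.2 says fostamatinib has not been used to treat COVID-19 before, and Section 9.1 says safety data in combination with standard of care are unavailable. Section 2.2 adds that the presentation of COVID-19 can overlap with the drug's toxicities. Single events will be hard to attribute, so the comparison between arms matters more than usual.

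For inpatients, detection is unlikely to be the slow step, because Section 8.3 has the study team assess adverse events daily. The 72 hours is then time between the site knowing and the DCC knowing. The count does not obviously need that time: as Section 9.3.6 describes it, the boundary compares deaths and SAEs by arm and does not mention causality. At stake is the number of patients randomised while a death is known at the site but not yet at the DCC.

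**Working it through.** **Inputs.** Accrual 25 per month (Section 5.6); enrolment over 2 to 3 months (synopsis); about 60 patients, 1:1 (Section 9.1); reporting limit 72 hours (Section 8.4.6). The 24-hour comparator is the limit proposed here; the documents do not give it. A month is taken as 30.44 days.

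**Step 1: the plan's own figure.** 60 / 25 = 2.4 months, which lies within the stated 2 to 3 months. The accrual rate and the enrolment period agree.

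**Step 2: daily rate.** 25 / 30.44 = 0.82 patients a day. If enrolment takes 2 months, 60 / (2 × 30.44) = 0.99 a day; if 3 months, 60 / (3 × 30.44) = 0.66 a day.

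**Step 3: patients randomised in each reporting window** (daily rate × days).

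| Enrolment period | Per day | In 72 hours | In 24 hours | Difference |
|---|---|---|---|---|
| 2 months | 0.99 | 3.0 | 0.99 | 2.0 |
| 2.4 months (25 per month) | 0.82 | 2.5 | 0.82 | 1.6 |
| 3 months | 0.66 | 2.0 | 0.66 | 1.3 |

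At 25 per month, the 72-hour figure is 2.46 / 60 = 4.1% of the trial (3.3% to 4.9% over the range).

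**Step 4: fostamatinib arm.** With 1:1 allocation, half of 2.46 is about 1.2 patients in 72 hours, and half of 0.82 is about 0.4 in 24 hours. The difference is about 0.8.

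**Step 5: chance that at least one patient is randomised in the window,** taking arrivals as Poisson (an assumption). 72 hours: 1 − exp(−2.46) = 91%. 24 hours: 1 − exp(−0.82) = 56%.

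These are worst-case figures for the reporting step. They assume that the report arrives at the last permitted moment. They leave out any delay before the site becomes aware, which could be longer for discharged patients once the daily calls end.

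**The case against.** The strongest reply is that the documents do not say what feeds the boundary. Deaths also appear in the daily in-hospital ordinal score (8 is death), and Section 8.4.4 puts SAEs in a research database. NHLBI is both coordinating centre and sponsor, and the NIH Clinical Center is itself an enrolling site. The looks, the boundary and the DSMB's data elements are left to a monitoring plan and charter that are not part of these documents (Sections 9.3.6 and 10.5). That plan may require immediate notice of deaths. It may also space the looks so widely that three days matters little.

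This stands as a limit on the claim. It does not remove the point: no data-entry deadline is given for the other routes, and the only site-to-DCC limit in the protocol is 72 hours. It is also true that 72 hours is a ceiling rather than a typical delay.

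A reader might infer more than the documents support:

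- **That the boundary will run three days behind.** This is possible, but the data feed and look schedule are not given.
- **That earlier notice would save doses**, up to 6 of the 28 in three days (3 × 2). Crossing the boundary leads to DSMB review and does not itself stop dosing or randomisation. The investigator can stop study drug for an SAE (Section 7.1) and, under stated conditions, unblind the patient (Section 6.3.2) without waiting for the DCC.
- **That the 72 hours adds to the 7-day Unanticipated Problem limit.** Both clocks start when the investigator knows, so they run together. A faster first notice would leave the 7 days unchanged.
- **That patients randomised in the window add nothing to the trial.** They still contribute to the primary endpoint, SAE incidence by arm.

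**Conclusion.** The point holds as a low-cost improvement to patient protection; no two parts of the plan contradict each other here. One 72-hour limit covers deaths and life-threatening SAEs, and the body that receives those reports must monitor a mortality and SAE boundary while enrolment continues.

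The size is modest. At 25 patients per month, a 24-hour limit would mean at most about 1.6 fewer patients randomised before the DCC knows (1.3 to 2.0 for enrolment over 3 to 2 months), about 0.8 of them on fostamatinib.

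This rests on three assumptions: the site reports at the limit, the boundary depends on these reports, and the event that matters is fatal or life-threatening. Even then the gain is earlier knowledge at the DCC. Whether fewer patients are enrolled depends on how quickly the DSMB acts. If the DSMB monitoring plan already requires faster notice of such events, the only gap is that the protocol text does not say so.

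**What to change.** In Section 8.4.6:

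- Require a short initial notice of every death and life-threatening SAE to the DCC/sponsor within 24 hours of site awareness, with the causality assessment and details to follow.
- State that these events count toward the Section 9.3.6 boundary on receipt of the notice.
- Keep 72 hours for all other SAEs.
- Align the rule with the DSMB monitoring plan. If that plan already sets a faster limit, say so in the protocol.

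The cost is a short addition to Section 8.4.6 and site training. The downside is that some first reports will be incomplete and need a follow-up form. The change is also partial: the boundary covers SAEs generally, and the SAEs that are neither fatal nor life-threatening would still arrive on the 72-hour limit.

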#### **Reports to the NHLBI Clinical Director**

Data Coordinating Center (DCC)/study sponsor (NHLBI) will refer to NHLBI DIR Policy to determine Clinical Director reporting requirements and timelines.

